8.3 Adverse Event Characteristics

CTCAE Term

(AE description) and grade: The descriptions and grading scales found in the NCI Common Terminology Criteria for Adverse Events (CTCAE) version 4.03 will be utilized for AE reporting. All appropriate treatment areas should have access to a copy of the CTCAE version 4.03. A copy of the CTCAE version 4.03 can be down loaded from the CTEP web site. (<http://ctep.cancer.gov>).

Attribution of the AE

The investigator or co-investigator is responsible for assignment of attribution.

Definite – The AE *is clearly related* to the study treatment

Probable – The AE *is likely related* to the study treatment

Possible – The AE *may be related* to the study treatment

Unlikely – The AE *is doubtfully related* to the study treatment

Unrelated – The AE *is clearly NOT related* to the study treatment

8.4 Serious Adverse Event Reporting Guidelines

The Principal Investigator must be notified within 2 business day of study team's knowledge of any event meeting the criteria and definition of a serious adverse event, regardless of attribution, occurring during the study or within 30 days of the last administration of the study related treatment.

The investigator must report all events meeting the criteria and definition of a serious adverse event that are unexpected and possibly related (definite, probable or possible) to study treatment within 7 business days of study team's knowledge if death or life threatening, and within 14 calendar days for all others. Events that meet the FDA reporting requirements will be reported to the FDA according to 21CFR312.32.if the study is conducted under an IND.

All Serious Adverse Events that are unexpected and possibly related (definite, probable or possible) to study treatment administration will be reported to the IRB using the OCTSU Serious Adverse Event form.

8.5 Routine Reporting

All other adverse events- such as those that are expected, or are unlikely or definitely not related to the study participation- are to be reported annually as part of regular data submission.

8.6 Reporting of Unanticipated Problems

There are types of incidents, experiences and outcomes that occur during the conduct of human subjects research that represent unanticipated problems but are not considered adverse events. For example, some unanticipated problems involve social or economic harm instead of the physical or psychological harm associated with adverse events. In other cases, unanticipated problems place subjects or others at increased risk of harm, but no harm occurs.

Upon becoming aware of any incident, experience, or outcome (not related to an adverse event) that may represent an unanticipated problem, the investigator should assess whether the incident, experience, or outcome represents an unanticipated problem. The incident, experience or outcomes is considered unanticipated if it meets all of the following criteria:

1. Unexpected (in terms of nature, severity, or frequency);
2. Related or possibly related to participation in the research; and
3. Suggests that the research places subjects or others at a greater risk of harm than was previously known or recognized.

If the investigator determines that the incident, experience, or outcome represents an unanticipated problem, the investigator must report it to the IRB within 7 calendar days of the study team becoming aware of the problem.

9.0 DRUG INFORMATION

9.1 Pembrolizumab (Keytruda®)

- Other names for the drug: Keytruda®
- Description: Injection: 100 mg/4 mL (25 mg/mL) solution in a single-dose vial
- Classification: type of agent: Immunomodulatory; checkpoint inhibitor
- Mode of action: Pembrolizumab is a monoclonal antibody that binds to PD-L1 and blocks its interactions with both PD-1 and B7.1 receptors. This releases the PD-L1/PD-1 mediated inhibition of the immune response, including activation of the anti-tumor immune response without inducing antibody dependent cellular cytotoxicity.
- Pharmacokinetics: Based on a population analysis that included 2,841 patients in various dose range, the typical population clearance was 212 mL/day, volume of distribution at steady state was 6.1 L, and the terminal half-life was 23 days. The population PK analysis suggests steady state is obtained by 19 weeks with an every 3-week regimen and the systemic accumulation was 2.2-fold. The systemic accumulation in area under the curve (AUC), maximum concentration (C_{max}) and trough concentration (C_{min}) of pembrolizumab increased dose proportionally in the dose range of 2 to 10 mg/kg every 3 weeks.
- Side effects: Please see the package insert(s) for pembrolizumab. For the most recent safety update, please refer to the current package insert(s).
- Drug Interactions Please see the package insert for pembrolizumab for information regarding drug interactions.
- Contraindications: Please see the package insert for pembrolizumab for information regarding contraindications.
- Special Warnings and Precautions for Use: Please see the package insert(s) for pembrolizumab for information regarding special warnings and precautions for use.
- Storage and stability: Store vials under refrigeration at 2°C to 8°C (36°F to 46°F) in original carton to protect from light. This product does not contain a preservative. Administer immediately once prepared. If diluted pembrolizumab infusion solution is not used immediately, it can be stored either:
 - At room temperature for no more than 6 hours from the time of preparation. This includes room temperature storage of the infusion in the infusion bag and time for administration for infusion.
 - Under refrigeration at 2°C–8°C (36°F–46°F) for no more than 24 hours. Do not freeze. Do not shake. If refrigerated, allow the diluted solution to come to room temperature prior to administration.
- Preparation and Dispensing:

Visually inspect drug product for particulate matter and discoloration prior to administration whenever solution and container permit. Pembrolizumab is a colorless to slightly yellow solution. Discard the vial if the solution is cloudy, discolored, or visible particles are observed. Do not shake the vial. Prepare the solution for infusion as follows: Add 2.3 mL of Sterile Water to vial. Withdraw the required volume of pembrolizumab from the vial and transfer into an intravenous (IV) bag containing 0.9% Sodium Chloride Injection, USP or 5% Dextrose Injection, USP. Mix diluted solution by gentle inversion. Do not shake. The final concentration of the diluted solution should be between 1 mg/mL to 10 mg/mL. Discard partially used or empty

vials of pembrolizumab.

- Administration:
Administer the initial infusion over 30 minutes through an intravenous line with or without a sterile, non-pyrogenic, low-protein binding in-line filter (pore size of 0.2–0.22 micron). If the first infusion is tolerated, all subsequent infusions may be delivered over 30 minutes. Do not co-administer other drugs through the same intravenous line.
- Availability: Commercially available through Merck & Co., Inc. Standard of care in metastatic platinum refractory urothelial carcinoma.

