5.0 TREATMENT PLAN

5.1 Treatment Dosage and Administration

Protocol treatment must start within 14 business days of enrollment to the study.

5.1.1 Therapy will include pembrolizumab 200 mg IV starting on day 1 in 21 day cycles. Patients will receive 1 dose (cycle 1) of pembrolizumab and commence SBRT no later than initiation of cycle 2.

5.1.2 SBRT will be given to ≥ 1 metastatic lesion(s) deemed most appropriate for such therapy by the treating radiation oncologist. SBRT will be delivered in 3 or 5 fractions with dose and fractionation selected to respect standard normal tissue dose constraints for adjacent organs at risk. See section 5.3 for further details.

5.1.3 The lesion to which SBRT is given will be identified after the patient receives 1 dose of pembrolizumab

5.1.3 Patients will be treated with supportive care pre-medications as clinically indicated including anti-emetics.

REGIMEN DESCRIPTION					
Agent	Premedications	Dose	Route	Schedule	Cycle Length
Pembrolizumab	None mandated	200 mg	IV	Once every 21 days (+/- 3 business days)	
SBRT	None mandated	3-5 fractions with dose and fractionation selected to respect standard normal tissue dose constraints for the relevant organs in the vicinity of the target lesion(s).	n/a	In cycle 1 any time after D1 and will commence no later than initiation of cycle 2	

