	
 • 1-2mg/kg/day methylprednisolone IV or IV equivalent • Add prophylactic antibiotics for opportunistic infections 	
--	--	--

5.2.1.7 Renal:

Rule out non-inflammatory causes. If non-inflammatory cause, treat accordingly and continue protocol therapy

Grade of elevation in serum creatinine (NCI CTCAE v4.03)	Management	Follow-up
Grade 1 Serum creatinine >ULN and >baseline but ≤1.5x baseline	
 • Continue pembrolizumab • Monitor serum creatinine weekly 	
 • If returns to baseline, resume creatinine monitoring per protocol • If worsens, treat as grade 2, 3, or 4
Grade 2 or 3 Serum creatinine 1.5x baseline to ≤ 6 x ULN	
 • Delay or discontinue pembrolizumab • Monitor serum creatinine every 2-3 days • 0.5-1 mg/kg/day methylprednisolone IV or oral equivalent • Add prophylactic antibiotics for opportunistic infections • Consider renal biopsy 	
 • If improves to grade 1 
 • Taper steroids over at least one month • Resume pembrolizumab if improves to ≤ grade 1 within 12 weeks and corticosteroids have been reduced to ≤ 10 mg oral prednisone or equivalent per day • If elevation persists >7 days or worsens, treat as grade 4
Grade 4 Serum creatinine <6x ULN	
 • Discontinue pembrolizumab • Monitor serum creatinine daily • 1-2mg/kg/day methylprednisolone IV or IV equivalent • Add prophylactic antibiotics for opportunistic infections • Consult nephrology • Consider renal biopsy 	
 • If improves to grade 1 
 • Taper steroids over at least one month • Resume pembrolizumab if improves to ≤ grade 1 within 12 weeks and corticosteroids have been reduced to ≤ 10 mg oral prednisone or equivalent per day

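### Section 9.1 tells staff to dilute a vial that already holds a ready 25 mg/mL solution, which makes the only stated vial concentration wrong at withdrawal

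*Combined protocol and SAP*

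**What the plan says.** Section 5.1.1 sets the dose: "Therapy will include pembrolizumab 200 mg IV starting on day 1 in 21 day cycles". Section 5.2 does not allow the strength of a dose to be altered.

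The description in Section 9.1 gives the presentation as "Injection: 100 mg/4 mL (25 mg/mL) solution in a single-dose vial". The preparation and dispensing paragraph of the same section agrees that the product is liquid: "Pembrolizumab is a colorless to slightly yellow solution". Its first preparation step is then "Add 2.3 mL of Sterile Water to vial". The next step is "Withdraw the required volume of pembrolizumab from the vial", for transfer to a bag of saline or dextrose. No figure in mL, number of vials, or in-vial concentration after the water is given. For the bag, the text says: "The final concentration of the diluted solution should be between 1 mg/mL to 10 mg/mL".

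Section 9.1 sends the reader to the package insert for side effects, interactions, contraindications and warnings. It does not do so for preparation, so nothing in the documents overrides the water step.

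On the separate query, the Grade 4 row of the renal table (Section 5.2.1.7) orders pembrolizumab to be discontinued. Its follow-up column allows pembrolizumab to resume if the event improves to grade 1 or better within 12 weeks and steroids are down to 10 mg of prednisone or less per day.

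**The concern.** A solution supplied at 25 mg/mL needs no water added to the vial. The sentence is complete and unredacted, so the contradiction does not come from how the text was extracted. It sits in an operative dosing instruction rather than in background text.

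What is at stake is the dose delivered. Without the water step, the volume to draw follows from the dose and the stated concentration. With it, that calculation gives too little drug, and the protocol supplies no replacement figure. The missing withdrawal volume is thus a consequence of the stray sentence, not a second fault.

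The renal row raises a different question: whether a patient with Grade 4 renal toxicity may be given pembrolizumab again.

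**Working it through.** **Inputs**
- Vial content: 100 mg in 4 mL (Section 9.1, description).
- Water added: 2.3 mL (Section 9.1, preparation).
- Dose: 200 mg (Section 5.1.1).
- Bag concentration: 1 to 10 mg/mL (Section 9.1, preparation).

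**The plan's own figure.** Concentration = mg / mL = 100 / 4 = 25 mg/mL, which matches the stated value. The volume for the dose is 200 / 25 = 8 mL, the full content of two vials.

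**After the water step**
- Volume per vial: 4 + 2.3 = 6.3 mL.
- Concentration: 100 / 6.3 = 15.87 mg/mL.
- Volume needed for 200 mg: 200 / 15.87 = 12.6 mL = 2 × 6.3 mL, again the full content of two vials.

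**Dose delivered, by how the volume is chosen**

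| Volume drawn | Dose delivered | Shortfall |
|---|---|---|
| 12.6 mL (both vials emptied) | 12.6 × 15.87 = 200 mg | 0% |
| 8 mL (computed at 25 mg/mL) | 8 × 15.87 = 127.0 mg | 1 − 127.0 / 200 = 36.5% |

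In the second case 12.6 − 8 = 4.6 mL stays in the vials, holding 200 − 127.0 = 73.0 mg.

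**Would the bag concentration reveal the difference?**
- 200 mg meets 1 to 10 mg/mL in 200 / 10 = 20 mL to 200 / 1 = 200 mL.
- 127 mg meets it in 127 / 10 = 12.7 mL to 127 / 1 = 127 mL.
- Any final volume from 20 to 127 mL therefore fits either dose.

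**Renal query, by comparison of the text.** No arithmetic applies.
- For plain discontinuation being final: the general rule in Section 5.2 uses "discontinue pembrolizumab" as the last step when a non-hematologic toxicity has not recovered in 12 weeks. Five other complete table rows that order plain discontinuation carry no resume line: colitis Grade 4, hepatic Grade 3-4, pancreatic Grade 4, neurological Grade 3-4, and meningitis or encephalitis.
- For it being reversible: Grade 4 hypophysitis and severe infusion reactions are marked as permanent stops, a word the renal row lacks. The Skin Grade 3-4 row, which includes life-threatening rash, offers delay or discontinuation and has a resume line with the same conditions.

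**The case against.** The strongest reply is that the 127 mg case needs two things together: the preparer adds the water, then computes the volume as though no water had been added. The dose is fixed at 200 mg and each single-dose vial holds 100 mg, so the natural act is to use two whole vials, which gives 200 mg with or without the water. The error would also leave 4.6 mL of the 12.6 mL behind, more than a third. The drug is commercially supplied and standard of care in this disease, so pharmacy routine may well prevent the mistake. All of this stands as a limit on likelihood. It does not remove the contradiction, and the documents do not say that pharmacy practice replaces the written step.

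A reader might infer that patients are expected to be underdosed by about a third. The documents do not support that, because the result depends on how the volume is chosen and they do not settle it.

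A reader might also infer that a protocol dose check fails. The 1 to 10 mg/mL range is a target for the diluted bag and is not presented as a check on dose, so its silence is not a failed safeguard. Likewise, the line beginning "Discard partially used or empty" is a disposal rule. It neither requires both vials to be emptied nor shows that partial use is expected.

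On the renal row, a reader might infer that the resume line is plainly the mistake. The five rows without such a line point that way, but the Skin Grade 3-4 row and the use of a permanent stop elsewhere point the other way. The documents do not decide it.

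**Conclusion.** The contradiction in Section 9.1 is certain and should be corrected. Followed as written, the water step turns 25 mg/mL into 15.9 mg/mL and makes the protocol's only vial concentration wrong at withdrawal. The dose delivered could then be anywhere from 200 mg (0% short) to 127 mg (36.5% short). The lower figure assumes that the water is added and that 8 mL is still drawn on the stated 25 mg/mL. It is a conditional worst case of unknown likelihood.

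This is a drug-preparation and patient-safety wording point, not a statistical one. A reader might infer a threat to the feasibility result, but the primary endpoint counts pembrolizumab doses or cycles and SBRT, not milligrams. No effect on the sample size, the 14-of-20 rule or the primary endpoint is claimed.

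The renal Grade 4 row is a separate request for clarification, with no preferred answer.

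**What to change.** 1. In Section 9.1, delete the sentence that adds water to the vial. State instead that 8 mL (4 mL from each of two 100 mg vials, 200 mg in total) is transferred to the IV bag, to a final volume of 20 to 200 mL so that the stated 1 to 10 mg/mL is met. Pharmacy should confirm the wording.
2. Separately, the investigator should decide whether renal Grade 4 toxicity in Section 5.2.1.7 is a final stop or a hold, and the row should keep only the matching instruction.

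The cost is a wording amendment: one sentence replaced in Section 9.1 and one table row clarified. Sample size, visits and analysis do not change.

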10.0 CORRELATIVES/SPECIAL STUDIES

10.1 Sample Collection Guidelines

Tumor tissue should be identified prior to registration. An archived formalin-fixed paraffin embedded tissue block and/or fresh tissue will be submitted for each subject from prior cystectomy or biopsy of metastatic lesion (estimated tumor content >30% of nucleated cells in specimen). This tissue may be used for:

- PD-L1 testing of tumor cells and tumor infiltrating immune cells
- Next generation sequencing via MI-ONCOSEQ
- Tumor immune infiltrate sequencing via CIBERSORT

Plasma sample (5-10mL) at baseline only:

- 5-10 mL will be banked
- See below for collection and processing instructions

Serum samples (5-10 mL) at baseline only:

- For banking
- See below for collection and processing instructions

Serum collection and processing

Collect whole blood in a covered test tube. If commercially available tubes are to be used, the researcher should use the red topped tubes. These are available from Becton Dickinson (BD). BD's trade name for the blood handling tubes is Vacutainer. After collection of the whole blood, allow the blood to clot by leaving it undisturbed at room temperature. This usually takes 15-30 minutes. Remove the clot by centrifuging at 1,000-2,000 x g for 10 minutes in a refrigerated centrifuge.

The resulting supernatant is designated serum. Following centrifugation, it is important to immediately transfer the liquid component (serum) into a clean polypropylene tube using a Pasteur pipette. The samples should be maintained at 2-8°C while handling. The serum should be apportioned into 0.5 ml aliquots, stored, and transported at –20°C or lower. It is important to avoid freeze-thaw cycles because this is detrimental to many serum components. Samples which are hemolyzed, icteric or lipemic can invalidate tests.

Plasma samples collection and processing

Collect whole blood into commercially available anticoagulant-treated tubes e.g., EDTA-treated (lavender tops) or citrate-treated (light blue tops). Heparinized tubes (green tops) are not permitted. Cells are removed from plasma by centrifugation for 10 minutes at 1,000-2,000 x g using a refrigerated centrifuge. Centrifugation for 15 minutes at 2,000 x g depletes platelets in the plasma sample.

The resulting supernatant is designated plasma. Following centrifugation, it is important to immediately transfer the liquid component (plasma) into a clean polypropylene tube using a Pasteur pipette. The samples should be maintained at 2-8°C while handling. If the plasma is not analyzed immediately, the plasma should be apportioned into 0.5 ml

aliquots, stored, and transported at –20°C or lower. It is important to avoid freeze-thaw cycles. Samples which are hemolyzed, icteric, or lipemic can invalidate certain tests.

Tissue samples and banked serum/plasma should be delivered for analysis/storage to:

Attention: [name], MS, MT (ASCP, CLsp (MB))
Michigan Center for Translational Pathology

[REDACTED]
Phone: [REDACTED]
Fax: [REDACTED]

10.2 Specimen Banking

Banked patient samples (tissue, blood, serum, plasma) collected for this study will be retained at the University of Michigan. Coded specimens will be stored indefinitely or until they are used up. If consent for future use of specimens is withdrawn by the subject, best efforts will be made to stop any additional studies and to destroy the specimens.

Specimens being stored long-term for potential use not outlined in the protocol are subject to University Policy Governing Tissue Sample Collection, Ownership, Usage, and Disposition within all UMMS Research Repositories [<http://msa.med.umich.edu/policies/tissue-sample-collection-ownership-usage-disposition-within-all-umms-research-biorepositories>].

11.0 STATISTICAL CONSIDERATIONS

11.1 Study Design/Study Endpoints, Sample Size and Accrual

The primary aim of this study is to determine the feasibility of treating patients with metastatic urothelial carcinoma who have progressed after platinum based chemotherapy with sequential pembrolizumab and SBRT. Treatment success will be defined as completion of 4 cycles of pembrolizumab and at least one course of treatment of SBRT within 15 weeks from first dose of pembrolizumab. The trial will define the combination treatment as feasible if 70% of the patients receive the treatment as defined. With 20 evaluable patients, if 14 out of 20 (70% [95% Confidence Interval: 50% - 90%]) achieve successful treatment then the trial will conclude that further evaluation of sequential pembrolizumab and SBRT should be explored. A patient is evaluable for feasibility and safety if they receive at least one dose of pembrolizumab. Patients who achieve a complete response prior to SBRT are not evaluable for feasibility. Non-evaluable patients will be replaced. With accrual of 1-2 patients per month the trial accrual is expected to take up to 24 months.

Secondary endpoints will include efficacy and safety. Efficacy will be measured using the following endpoints: best overall response by RECIST and Immune Related Response Criteria and progression-free survival by RECIST and Immune Related Response Criteria. Safety endpoints will measure the frequency and severity of grade 3-5 drug-related adverse events of the combination of SBRT and pembrolizumab.

Correlative plans are described separately below.

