2.2 Secondary Objectives

1. To determine the safety of the combination of SBRT and pembrolizumab in patients with platinum-refractory metastatic urothelial carcinoma.
2. To determine the anti-tumor efficacy of the combination of SBRT and pembrolizumab in patients with platinum-refractory metastatic urothelial carcinoma.

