7.0 MEASUREMENT OF EFFECT

7.1 Antitumor Effect- Solid Tumors

Response and progression will be evaluated in this study using the new international criteria proposed by the Response Evaluation Criteria in Solid Tumors (RECIST) Committee [JNCI 92(3):205-216, 2000]. Changes in only the largest diameter (unidimensional measurement) of the tumor lesions are used in the RECIST v1.1 criteria.

Definitions

Evaluable for toxicity. All patients will be evaluable for toxicity from the time of their first treatment with study drug.

Evaluable for objective response. Only those patients who have measurable disease present at baseline, have received at least 1 dose of pembrolizumab and have had their disease re-evaluated will be considered evaluable for response. These patients will have their response classified according to the definitions stated below. (Note: Patients who exhibit objective disease progression prior to the end of cycle 1 will also be considered evaluable.)

Disease Parameters

Measurable disease. Measurable lesions are defined as those that can be accurately measured in at least one dimension (longest diameter in the plane of measurement is to be recorded) with a minimum size of:

- 10mm by CT scan (irrespective of scanner type) for studies with a slice thickness of ≤ 5 mm or twice the slice thickness or MRI
- 10mm caliper measurement by clinical exam (lesions which cannot be accurately measured with calipers should be recorded as non-measurable)
- 20mm by chest X-ray (if clearly defined and surrounded by aerated lung)

All tumor measurements must be recorded in millimeters (or decimal fractions of centimeters)

Malignant lymph nodes: To be considered pathologically enlarged and measurable, a lymph node must be ≥ 15 mm in short axis when assessed by CT scan (CT scan slice thickness recommended to be no greater than 5 mm). At baseline and in follow-up, only the short axis will be measured and followed.

Non-measurable disease. All other lesions (or sites of disease), including small lesions (longest diameter <20 mm with conventional techniques or <10 mm using CT scan), are considered non-measurable disease. Bone lesions, leptomeningeal disease, ascites, pleural/pericardial effusions, lymphangitis cutis/pulmonis, inflammatory breast disease, abdominal masses (not followed by CT or MRI), and cystic lesions are all non-measurable.

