7.3 Safety/Tolerability

Analyses will be performed for all patients having received at least one dose of study drug. The study will use the CTCAE version 4.03 for reporting of non-hematologic adverse events (<http://ctep.cancer.gov/reporting/ctc.html>) and modified criteria for hematologic adverse events.

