11.2 Data Analyses Plans

The primary analysis will report the count, proportion and corresponding 95% binomial confidence interval of evaluable patients who completed 4 cycles of pembrolizumab and at least one course of treatment of SBRT within 15 weeks from first dose of pembrolizumab.

The best overall response (CR + PR) by RECIST and Immune Related Response Criteria will be reported separately with counts, proportions and corresponding 95% binomial confidence intervals. Progression-free survival endpoints will be described with medians and Kaplan-Meier plots using product-limit estimates and associated 95% confidence intervals using RECIST and Immune Related Response Criteria separately. Frequency and severity of drug-related adverse events will be described. Each of the secondary endpoints will be described in the evaluable population and in the population who achieve treatment success as defined in the primary endpoint.

Correlative Analyses

PD-L1 expression on tumor cells and immune cells infiltrating tumor, and CIBERSORT/TIMER gene expression profiling correlatives will be analyzed with association to clinical outcomes using exact chi-square tests, t-tests, or Kaplan-Meier methods as is appropriate for each independent covariate and clinical outcome. Tumor mutational status and burden by tissue based next generation sequencing (MI-ONCOSEQ) results will be descriptive.

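### The safety objective is the combination, but no planned analysis covers all SBRT-exposed patients or separates events before SBRT from those after it

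*Combined protocol and SAP*

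**What the plan says.** Section 2.2 states the first secondary objective: "To determine the safety of the combination of SBRT and pembrolizumab in patients with platinum-refractory metastatic urothelial carcinoma". Section 11.1 repeats the target: "Safety endpoints will measure the frequency and severity of grade 3-5 drug-related adverse events of the combination of SBRT and pembrolizumab".

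The safety population is defined in five places, each time by drug exposure alone. Section 11.1 has "A patient is evaluable for feasibility and safety if they receive at least one dose of pembrolizumab", and section 5.10 says the same. Section 7.3 has "Analyses will be performed for all patients having received at least one dose of study drug". Section 7.1 has "All patients will be evaluable for toxicity from the time of their first treatment with study drug". Section 5.2 also makes one pembrolizumab dose sufficient for toxicity evaluability. None of them mentions SBRT.

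Under section 5.1.1 SBRT follows the first dose and must begin by the start of cycle 2. Footnote 3 of the calendar in section 6.2 bars it from C1D1. Section 8.1 collects adverse events from the first study treatment.

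Section 11.2 then plans two populations: "Each of the secondary endpoints will be described in the evaluable population and in the population who achieve treatment success". Success is defined in section 11.1 as "completion of 4 cycles of pembrolizumab and at least one course of treatment of SBRT within 15 weeks from first dose of pembrolizumab".

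**The concern.** The objective names the combination, and the main safety set does not require it. A patient who leaves after one dose, before any SBRT, stays in the denominator. A drug-related event in the lead-in of up to about three weeks counts in the numerator. The reported grade 3-5 proportion therefore mixes pembrolizumab-alone with combination experience, and no planned table lets a reader separate the two.

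The second population looks like the remedy, because everyone in it was irradiated. But entry depends on having tolerated four cycles on time, so it can lose patients because of the toxicity being measured. A follow-on trial would probably take its safety assumption for the combination from one of these two tables, and neither describes all patients who received both treatments.

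**Working it through.** **The plan's own figure.** No safety figure is stated. The one computed result is 14/20 = 70% with a 95% interval of 50% to 90%. The Wald formula reproduces it: 0.70 ± 1.96 × √(0.70 × 0.30 / 20) = 49.9% to 90.1%. The exact interval is 45.7% to 88.1%. Intervals below are exact.

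**The sets side by side.**

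| Set | Entry rule | All irradiated patients included? | Never-irradiated patients included? | Pre-SBRT events separated? |
|---|---|---|---|---|
| Evaluable (5.2, 5.10, 7.1, 7.3, 11.1) | one pembrolizumab dose | yes | yes | no |
| Treatment success (11.1, 11.2) | four cycles plus SBRT within 15 weeks | no | no | no |
| Target of objective 1 | both treatments received | yes | no | yes |

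Neither planned set matches the third row.

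**Why the success set selects on toxicity.** Discontinuation is required for grade 3-4 pneumonitis (5.2.1.1), liver test elevation (5.2.1.4), neurological toxicity (5.2.1.6) and infusion reactions (5.2.1.8). Section 5.2 generally holds pembrolizumab for related non-hematologic toxicity of grade 2 or higher, and allows up to 12 weeks from the prior dose for recovery. The window leaves limited slack:

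- 15 weeks = 105 days.
- The fourth dose is due 3 × 21 = 63 days after the first, leaving 105 − 63 = 42 days.
- If four completed cycles are meant, 4 × 21 = 84 days, leaving 105 − 84 = 21 days.
- A hold of the longest permitted length makes one dose 84 − 21 = 63 days late, which exceeds either allowance.

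So both stopping and a long hold can remove an irradiated patient from the success set.

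**Illustration.** The documents give no number irradiated and no event count. I assume 20 treated, 18 irradiated, 14 successes, and 4 irradiated patients with a qualifying event after SBRT, with none in unirradiated patients.

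- Exposed rate: 4/18 = 22.2% (6.4% to 47.6%).
- Evaluable set: 4/20 = 20.0% (5.7% to 43.7%).
- Success set, if *k* of the 4 patients with events fail to complete four cycles in time: (4 − *k*)/14.

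| *k* | Success-set rate |
|---|---|
| 0 | 4/14 = 28.6% |
| 1 | 3/14 = 21.4% |
| 2 | 2/14 = 14.3% (1.8% to 42.8%) |
| 3 | 1/14 = 7.1% |
| 4 | 0/14 = 0% (0% to 23.2%) |

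For *k* of 1 or more, both planned figures fall below 22.2%, so they do not bracket the exposed rate. For *k* = 0 the success set overstates it.

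**Range for dilution alone.** With the same 4 events, the evaluable figure stays at 20.0%. The exposed rate is 4/20 = 20.0%, 4/18 = 22.2%, 4/16 = 25.0% or 4/14 = 28.6% as the number irradiated falls from 20 to 14.

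**The other direction.** With 18 irradiated, if one further patient had only a pre-SBRT event, the evaluable figure would be 5/20 = 25.0%, above 22.2%. The all-treated figure can therefore err either way.

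**The case against.** The all-treated set is a defensible choice. The regimen is sequential by design, with one pembrolizumab dose before SBRT, so lead-in toxicity belongs to the strategy a patient starts, including toxicity that prevents SBRT. The sections that define the set agree with one another. This stands: the table should stay, and a table restricted to irradiated patients should not displace it, because that restriction depends on a post-baseline event.

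A reader might infer that no planned analysis looks at SBRT-exposed patients at all. The documents do not support that. Section 11.2 describes every secondary endpoint, safety included, among treatment successes, all of whom received SBRT. The gap is narrower: that group is not all of the irradiated patients, and tolerating treatment is part of its entry rule.

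A reader might also take the 6 failures tolerated by the 14-of-20 threshold as 6 patients who missed SBRT. That too is unsupported. SBRT must begin by cycle 2, while the four-cycle requirement runs on for weeks, so many failures could come after irradiation. The 4/14 end of the range is an upper bound for a trial that just meets the threshold.

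Patients with a complete response before SBRT leave the feasibility set only. With the first on-treatment scan scheduled at week 12, such a response is unlikely to be documented, so this route adds little.

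Finally, safety is a secondary, descriptive endpoint in a 20-patient study and does not enter the feasibility decision. That limits the consequence but does not close the gap. An onset split also cannot isolate combination toxicity fully, since delayed effects of the first dose may appear after the first fraction.

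**Conclusion.** The point holds in a limited form. The plan has a safety table for everyone who started pembrolizumab and one for those who completed the regimen on time. It has none for everyone who received both treatments, and none that divides events at the start of SBRT. Both planned figures can understate the rate in irradiated patients: 20.0% and 14.3% against 22.2% in the illustration. That result rests on assumed counts of 18 irradiated, 14 successes and 4 patients with events, two of whom stopped early.

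These differences of 2.2 and 7.9 points are small beside exact intervals roughly 40 points wide, and nothing in the documents fixes their actual size. This is not an error in the all-treated set and does not affect the 14-of-20 rule. It is a cheap improvement that would let the trial address its own first secondary objective.

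**What to change.** Keep the all-treated table as a main safety result. Add to section 11.2 a descriptive table for all patients who received pembrolizumab and at least one SBRT fraction. It should give the number and proportion, with exact 95% interval, who had a grade 3-5 treatment-related event with onset on or after the first fraction. List events before the first fraction separately.

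State that treatment-related covers pembrolizumab or SBRT, using the attribution to study treatment in section 8.3. The drug-related wording in sections 2.4, 11.1 and 11.2 leaves the status of SBRT-attributed events open. A row for drug-related events alone would keep the new table comparable with the all-treated one.

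Present the two tables side by side, and add a sentence that the treatment-success table is not to be read as the safety of the combination.

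The cost is one extra table. Adverse event onset and SBRT timing are already needed for section 8.1 and the 15-week endpoint. The smaller denominator widens the interval slightly: in the illustration, 6.4% to 47.6% for 4/18 against 5.7% to 43.7% for 4/20. Design, sample size and treatment are unchanged.
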